10 EVALUATION OF FEASIBILITY

10.1 Assessment of Feasibility of Intervention

- In order to assess the feasibility of the intervention, the following questions must be answered: “Is the intervention tested in the pilot trial realizable, was it accepted by participants and considered usable (see below)?” To answer these questions, the following persons’ points of view were examined:

Medical assistant’s point of view: A focus group will be conducted on the realizability of the intervention. The content of a tape recording of the group meeting will be analyzed in terms of the main question: “What problems cropped up with the intervention, how severe were they considered to be and what changes did participants consider needed to be made to the intervention?” Further questions concerned the usability (usability: easy to learn, easy to memorize, efficient usability, low error rate, provides satisfaction to user ³⁶).

GP’s point of view: Short interviews will be held with the GP which concern the feasibility of the intervention and important changes in comparison to standard treatment. These interviews will be recorded and their content analyzed in terms of the main questions. “Is the intervention in its current form usable (see above), what barriers can be identified and what changes need to be made to the intervention?”

Patient’s point of view: At the T1 time of collecting data and as part of the telephone interview, a short guideline based survey takes place of the imposition caused by the intervention, the acceptance of the interview with the medical assistant as part of the brown bag review, and the perceived content of the doctor-patient interview. Pre-formulated answer categories will be quantitatively measured and analyzed. Open answers will be combined to create categories on the basis of content analysis.

11 DURATION OF TRIAL / TRIAL DROP-OUTS

11.1 End of Trial

The regular end of the trial is reached when the post-procedure observation period of three months is over for all patients participating in the trial.

11.2 Trial drop-outs

11.2.1.1 Patients drop out of trial

Patients have the right to drop out of the trial without giving reasons at any time and without losing the right to further treatment from the investigator. If a patient does not arrive to an appointment, the investigator must follow up the case until he has found out why the patient did not turn up. The investigator must try to complete and document all the examinations designated in the protocol.

If the patient only wishes to end the therapy measures foreseen in the trial but is happy for the further documentation of the course of his illness(es) to take place, then it is regarded as a drop out of therapy. The documentation will continue in accordance with the protocol (intention-to-treat principle).

11.2.1.2 Belated detection of exclusion criteria

If it belatedly turns out that a patient satisfied an exclusion criterium at the time of recruitment, then the fact must be documented on the relevant patient registration form. The protocol will nevertheless be continued for the patient as long as the newly discovered circumstance does not represent a risk or unacceptable stress for the patient.

11.2.1.3 Drop out of trial for individual patients The investigator can elect to remove a patient from the trial

- If following the protocol would represent unacceptable stress for the patient because of his situation (that may have to do with the development of his disease),
- If the patient moves to a nursing home and it is technically or organizationally no longer possible to conduct further telephone interviews
- If the patient changes to another GP and leaves the trial site.

If the course of events is foreseeable or can be planned a follow-up survey should be brought forward.

The Trial HQ must be informed of the withdrawal by fax and will confirm it. In case of a withdrawal, the reasons/circumstances and the most recent status must be documented. If the patient does not withdraw his declaration of consent, his survival status or a hospital stay should be documented at the end of the regular observation period.

11.2.2 Withdrawal of trial site from trial

The trial administrators can decide to withdraw a trial site (GP practice) from the trial if:

- It does not satisfy the protocol's technical requirements (e.g. organizational problems in implementing the protocol))
- The implementation of the trial is inadequate for the trial
- The quality of the data is inadequate
- The investigator withdraws his agreement to participate in the trial protocol

12.2 Statistical analysis

The primary analysis takes place for all target criteria according to the Intention-to-Treat (ITT) principle. Additional per-protocol analyses will be undertaken as sensitivity analysis.

The primary comparison between the intervention and the control group will be made on the basis of the difference between the MAI score at baseline (T0) and the MAI score after 6 weeks (T1). The primary comparison will thus be performed using a comparison between 2 mean values. Assuming a normal distribution and the same standard deviation in both groups, a two-tailed, unpaired t-test with a significance level of $\alpha = 0.05$ will be used. For the difference between mean values, a two-tailed 95% confidence interval will be specified. Furthermore, in order to quantify a possible cluster effect an intra-class-correlation (ICC)-coefficient (ICC) will be estimated. The ICC will be used for adjustment purposes as part of a multilevel regression analysis. The ICC estimate will also serve to prepare the sample size calculation for the planned main trial.

As this is a so-called pilot trial, the analysis of all result parameters will remain primarily descriptive. At the same time, the p-values will only have a descriptive character. Statistically significant differences (with a significance level of $\alpha = 0.05$, two-tailed) between the control and intervention groups will not be interpreted as proof of the effectiveness of the intervention. They serve merely to provide indications of irregularities in order to evaluate the suitability of the MAI score as a main target criterium and possibly identify further suitable target parameters for the planned main trial.

The statistical and biometric approaches and procedures to be used will be determined in detail in the statistical analysis plan.

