1.4 Synopsis of Protocol

[figure not shown]
title of Trial:	Prioritization and Optimisation of Multimедication in elderly, multimorbid patients in general practice
Abbreviated name of trial	PRIMUM Pilot - Pilot trial on Prioritization of Multimедication in Multimorbid patients
Sponsor	Johann Wolfgang Goethe University, Frankfurt am Main
Head of Clinical Trial	Dr. med. [name]
Indication:	Multimедication in elderly, multimorbid patients: Age ≥ 65 , ≥ 3 chronic diseases, ≥ 5 long-term medicines
Rationale	
 1. Multimorbidity, multimедication and increasing age raise the risk of inappropriate prescriptions and adverse drug events 2. Multimедication and high complexity of medication reduce adherence among patients 3. Doctor patient interviews on problems related to medicines are dominated by doctors in content and focus mostly on effectiveness 4. Patients do not generally inform doctors of adverse drug reactions and autonomous decisions to adjust medication dose 
(1) Use of pharmaceutical information system (AiD+) reduces number of inappropriate prescriptions (pharmaceutical interactions, renal dose adjustments, duplicate prescriptions)
 
(1-4) Take records of medicines that were actually taken and problems relating to medicines (technical handling, potential adverse drug reactions) by medical assistant provides structured information for the family doctor and enables patients to discuss their problems with the doctor.
 
→ Prescriptions become more appropriate → Prescriptions become less complex → Prescriptions take the patient's perspective into account (avoidance of adverse drug reactions, patients' preferences are taken into account) and prioritised → Patients are more satisfied with the information they receive and adhere to the doctor's therapy

Trial design:	Pilot trial, two armed, controlled, open, cluster-randomized (Randomization and intervention on the general practice level (HA-Praxen), measurement of outcomes on patient level, blind evaluation

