
	
 ▪ Satisfaction of patients with information provided on medicines 4. Quality of life, preservation of functional status ▪ General quality of life (EuroQuoL) ▪ WHO Disability Assessment Schedule (WHO-DAS II) 5. Pain ▪ Verbal Rating scale (VRS) 6. Days in hospital 7. Number (and type) of adverse drug reactions(ADR)
Potentially disruptive factors	
 ▪ Age ▪ Gender ▪ Additional prescribers in treatment process ▪ Depressivity (Geriatric Depression Scale, GDS) ▪ Co-morbidity: Cumulative Illness Rating Scale (CIRS), Charlston-Comorbidity-Index ▪ Infirmity (Sherbrooke Questionnaire)
Biometrics	
 - Descriptive and according to the intention to treat principle - Additional evaluation per protocol in form of sensitivity analyses - Regression for effects of covariables - All analyses include correction for cluster effect
Schedule:	
 - Begin of pre-phase for the development of Drug Information Service +, all trial plans and implemented instruments 01.01.09 - Begin of practice recruitment 01.02.09 - Begin of trial (sponsorship begins) 01.03.09 - Vote from Ethics Commission 16.03.09 - Begin of patient recruitment 01.05.09 - Duration of trial three months per patient - Deadline for interim report 01.12.09

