12.3 Reason for the sample size

The suitability of the Medication Appropriateness Index as a potential primary outcome criterium in the planned main trial should be checked. According to Browne³⁷ in Lancaster et al.³⁸ In order to have a good estimate of mean and standard deviation, 30 patients per group should be sufficient to test the suitability of a criterium. To ensure this target is definitely achieved, 50 patients will be recruited for the control group and 50 for the intervention group, thus making a total of 100 samples $N=100$.

With targeted cluster sizes of 5 patients per cluster, 10 GP practices will be needed for the intervention and 10 for the control group. This sample size will also make possible the calculation of intra-class-correlation coefficients (ICC) that is required for planning the sample size calculation.

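### The primary MAI comparison and its 95% CI rest on an unpaired t-test with no cluster term, although practices are randomised and the synopsis promises cluster correction throughout

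*Protocol*

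**What the plan says.** The synopsis (protocol section 1.4, trial design) describes a cluster-randomised pilot: "Randomization and intervention on the general practice level (HA-Praxen), measurement of outcomes on patient level, blind evaluation". Section 12.3 fixes the size: "With targeted cluster sizes of 5 patients per cluster, 10 GP practices will be needed for the intervention and 10 for the control group". That makes 50 patients per arm.

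Section 12.2 defines the primary comparison as one between two means of the MAI change from T0 to T1. The method is "Assuming a normal distribution and the same standard deviation in both groups, a two-tailed, unpaired t-test" with a two-sided level of 0.05. The interval follows directly: "For the difference between mean values, a two-tailed 95% confidence interval will be specified". Neither the test nor the interval carries a cluster term.

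The section then moves on, with a linking word that marks an addition, to estimating an ICC in case there is a cluster effect. It continues: "The ICC will be used for adjustment purposes as part of a multilevel regression analysis". This regression is not called primary.

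The synopsis, under Biometrics, says something different: "All analyses include correction for cluster effect".

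**The concern.** Patients of one practice share a doctor, and in the intervention arm also a trained assistant, so their MAI changes may be correlated. An unpaired t-test that counts each patient as independent then gives a standard error that is too small, an interval that is too narrow and a p-value that is too low. A comparison of this kind also breaks the synopsis rule on cluster correction.

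What is at stake is the purpose of the pilot. Section 12.2 uses significant group differences as pointers for judging the MAI as main-trial endpoint and for finding other candidates. The synopsis plans a between-group effect size for the MAI. Section 15.5 makes a favourable appraisal of the interim report a condition for the main-trial application. Precision that is overstated at this step can mislead those decisions.

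**Working it through.** **Unit of analysis.** Section 12.2 does not name the unit of the t-test. Three things point to the patient: outcomes are measured on patients (section 1.4), the sample size is counted as 50 patients per group (section 12.3), and the ICC enters section 12.2 only after the test and interval are complete.

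**Inputs from the protocol.** k = 10 practices per arm (sections 7.2 and 12.3); m = 5 patients per practice, as a target (section 12.3); two-sided level 0.05 and 95% interval (section 12.2). The plan's own total is reproduced: 2 × 10 × 5 = 100.

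**Assumed input.** The protocol gives no ICC. The relevant one is that of the MAI change. A range of 0.01 to 0.20 is assumed, with 0 as reference.

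**Formulas.**
- Design effect: DE = 1 + (m − 1) × ICC = 1 + 4 × ICC.
- Understatement of the standard error: 1 − 1/√DE.
- Approximate true size of the nominal 5% test: 2 × [1 − Φ(1.96/√DE)]. Example for ICC 0.10: DE = 1.4, 1.96/√1.4 = 1.66, size 9.8%.
- Ratio of interval half-widths, practice-means analysis to t-test on patients: (t with 18 df × √DE)/(t with 98 df).

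The size was also simulated: 100,000 trials per ICC, normal data, no true difference, 10 against 10 practices of five.

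| ICC | DE | SE understated by | Size, formula | Size, simulated | Coverage of nominal 95% CI | Half-width ratio |
|---|---|---|---|---|---|---|
| 0 | 1.00 | 0% | 5.0% | 4.9% | 95.1% | 1.06 |
| 0.01 | 1.04 | 2% | 5.5% | 5.4% | 94.6% | 1.08 |
| 0.05 | 1.20 | 9% | 7.4% | 7.3% | 92.7% | 1.16 |
| 0.10 | 1.40 | 15% | 9.8% | 9.8% | 90.2% | 1.25 |
| 0.20 | 1.80 | 25% | 14.4% | 14.6% | 85.4% | 1.42 |

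A separate simulation of 40,000 trials gave 7.1%, 9.7% and 14.4% at ICC 0.05, 0.10 and 0.20, hence the rounded 14–15% and 85–86% for the upper end. In the larger simulation a t-test on the 20 practice means (18 df) kept its size at 4.9% to 5.1% at every ICC tried.

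**The two passages side by side.** The synopsis requires cluster correction of every analysis. Section 12.2 gives the comparison it labels primary none, and puts the correction into a further analysis. No sentence ranks the two results. This conflict does not depend on the ICC.

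**The case against.** Four points can be made for the plan.

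1. Section 12.2 states that the analysis is mainly descriptive, that p-values are descriptive only, and that significance will not count as proof of effectiveness. This stands, and it limits the harm. A reader might infer that the plan risks a false claim of efficacy; the text rules that claim out.

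2. Clustering is not overlooked. The same section plans an ICC and a multilevel regression, and the synopsis commits to correction. This also stands, so it would be wrong to say that the protocol ignores clustering. The gap is narrower: the analysis called primary, and its interval, are uncorrected, and the order of precedence is left open. Section 12.2 leaves details to the statistical analysis plan, but the test, level and interval are already fixed here. An analysis plan with a different primary test would depart from the protocol.

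3. The unit is never named, and a t-test on practice means would fit the words. That is possible, so the patient-level reading remains an inference, though a well-supported one. If practice means were intended, the wording still needs to say so.

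4. The effect may be small. At ICC 0.01 the true error is about 5.4%. With equal practice sizes the estimated mean difference is the same either way, and the mean, SD and ICC carried into the main-trial sample size do not use this p-value. All of this is correct. But the protocol treats the ICC as unknown and gives no ground for assuming a low value, and it does give significance a role in judging endpoints.

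**Conclusion.** The point holds: as written, section 12.2 attaches the primary p-value and 95% interval to a method that does not match the randomisation, and it disagrees with the synopsis. Over an assumed ICC of 0.01 to 0.20, with five patients in each of 10 practices per arm, the true error of the nominal 5% test is about 5.4% to 14–15%, and coverage of the nominal 95% interval about 94.6% to 85–86%. The size rests on that assumed range and on the patient-level reading; the conflict with the synopsis rests on neither the ICC nor the simulation.

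The consequence is overstated precision and too many apparent signals when the MAI and other endpoints are judged for the main trial. In a pilot with descriptive p-values and a multilevel analysis already planned, this should be corrected, but it does not undermine the trial.

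**What to change.** In section 12.2, name the multilevel model that is already planned as the primary comparison of the MAI change. Specify a random practice intercept and Kenward-Roger or Satterthwaite degrees of freedom, and take the primary 95% interval from this model. Section 12.2 then agrees with the synopsis, and the question of which result prevails is settled.

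A t-test on the practice means (18 df with all 20 practices) can be kept as a simple check. It should not be presented as interchangeable with the model. The two agree only if practices contribute equal numbers (and the practice variance is not estimated as zero), whereas five per practice is a target, patients may drop out (section 11.2) and missing data are not replaced (section 12.4).

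The cost is one paragraph of wording and no additional data. The interval becomes wider: with the practice-means analysis as guide, by a factor of about 1.08 at ICC 0.01 and 1.42 at ICC 0.20. Even with no clustering it would be about 1.06 times as wide, because 18 rather than 98 degrees of freedom are used.

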12.3 Reason for the sample size

The suitability of the Medication Appropriateness Index as a potential primary outcome criterium in the planned main trial should be checked. According to Browne³⁷ in Lancaster et al.³⁸ In order to have a good estimate of mean and standard deviation, 30 patients per group should be sufficient to test the suitability of a criterium. To ensure this target is definitely achieved, 50 patients will be recruited for the control group and 50 for the intervention group, thus making a total of 100 samples $N=100$.

With targeted cluster sizes of 5 patients per cluster, 10 GP practices will be needed for the intervention and 10 for the control group. This sample size will also make possible the calculation of intra-class-correlation coefficients (ICC) that is required for planning the sample size calculation.

12.4 Missing data

Missing data will not be replaced.

13 DOCUMENTATION, DATA MANAGEMENT AND ARCHIVING

13.1 Documentation concept

13.1.1 Patient registration forms and patient inclusion

The patient registration form will be faxed to the Trial HQ. It includes the patients' names and telephone numbers (so that the interviews can be conducted in a timely manner) as well as other information on in- and exclusion criteria and on the availability of informed consent.

At Trial HQ, these data will be entered into a separate databank (Access™) from which personal data will be deleted after conclusion of the trial.

13.1.2 Data collection following patient inclusion

1. Case Report Form (CRF)

The CRF is a paper-based document that is completed at visits T0, T1 and T2 and records the following variables:

- **Basic clinical data:** Sociodemographic detail, physical examination (height, weight), current diagnoses, allergies / intolerances and hospitalization during the last six months, laboratory tests (serum electrolytes, serum creatinine)
- **Current medication:** prescription drugs and OTC drugs recommended by the doctor (active ingredient or trade name, strength, dosage form), indications, duration of therapy and estimation of importance of the medication relative to the therapy concept as a whole.
- **CIRS-Value:** modified Cumulative Illness Rating Scale (1 extra item, 1 additional answer category)
- Expanded **Charlston Comorbidity Index**

The CRF is completed by the investigator¹. Every CRF includes a sheet of paper with information on filling in the form and a checklist on how to send the to data (see below). Necessary correction to the CRF must take place in the following manner: invalid data should be crossed out whereby crossed-out details should be authorized with the date and the investigator's initials.

¹ Werden klinische Basisdaten, Scores psychometrischer Instrumente und Medikation durch eine dafür geschulte MFA erhoben, bestätigt der Prüfarzt die Richtigkeit der Angaben mit seiner Unterschrift.

2. Patient questionnaire

The patient questionnaire is also on paper and is also filled in at visits T0, T1 and T2.. It covers the following information:

- Quality of life (EuroQoL)
- WHO Disability Assessment Schedule (WHO-DAS II)
- Beliefs about Medicines Questionnaire (BMQ)
- Medication adherence (MARS)
- Verbale rating scale on pain (VRS)

The patient questionnaires, including an envelope, will be issued by the medical assistants. The patients fill in the questionnaires in the practice and put them in the envelopes which they then seal themselves (confidentiality of information with respect to trial site). If necessary, the medical assistants provide help filling in the patient questionnaires and keep an eye on the return of the completed documents.

The completed CRFs and the sealed envelope with the completed patient questionnaire will be put in the return envelopes (no stamp required) at the trial site and returned to the Trial HQ.

3. Patient telephone interview

After the arrival of the patient registration forms, the participating patients will be called on the telephone by a trained trial employee - firstly at the time of the T0 visit and then at the regular T1 and T2 - visits and asked about the following:

- Medication, Allergies, adverse drug reactions
- Hospitalization
- Sherbrooke questionnaire
- Depression (GDS)
- Medication adherence according to Morisky

The information will be entered directly into an SQL-database (Access™).

13.2 Data management

The completed CRFs will be sent by post to Trial HQ. The due dates for sending the documentation is described in a guideline on data flow in the investigator's file. The responsible trial employee will check all incoming post is complete and confirm receipt by marking it (date of receipt, date of check, initials). Missing information will be collected in preparation for the following query management (see below).

The data whose receipt has been confirmed will then be entered into an SQL trial database (Access™) by one of the trial employees. A data check will take place of this database according to specific trial rules (range-, Validity, and consistency checks according to defined SOPs developed during the course of the trial and documented in the TMF). Queries for the investigators that may crop up as a result of this data check will be formulated by Trial HQ (see below, Query management). With the exception of the patient registration form which is recorded separately, sending, collecting and processing patient data will always take place under the patient identification number (Pat.-ID) pseudonym.

Coding will be used for some of the data, partly when the data is entered. In retroactive processing steps, some free text information will be encoded into new variables. The encryption specifications will be deposited in the TMF

